## Introduction

This statistical analysis plan (SAP) details the statistical procedures to address the Primary and Secondary Objectives for the WIMS study.

## Study Objectives and Summary

Protocol title:	Wireless Physiologic Monitoring Among Postpartum Women
Design:	Single site, prospective pragmatic type 2 hybrid effectiveness-implementation trial utilizing a quasi-experimental, interrupted time series with repeated on/off periods
Study arms:	Repeated on/off intervention-control periods in 2-week blocks. Intervention group to receive wireless monitoring, and Control group to receive standard of care.
Population:	Women aged 18 and older undergoing emergency cesarean delivery at MRRH
Sample size:	Approximately 1266 women (633 per arm); dependent on clinical volume during blocks
Study sites:	Mbarara Regional Referral Hospital, Mbarara
Aim 1:	To estimate the clinical effectiveness of wireless physiologic monitoring of women in the first 24 hours after cesarean delivery at a referral hospital in a RLS.
Aim 2:	To evaluate the clinical adoption of wireless physiologic monitoring in a RLS using an implementation science approach using the RE-AIM Implementation framework.
Aim 3:	To use qualitative methods to explore clinical adoption by doctors and acceptability of wireless physiologic monitoring among postpartum women in RLS and understand facilitators and barriers to uptake of wireless physiologic monitoring.

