Research assistants will be asked to document field notes at the time of consent to capture information on the length of time taken for the consent, if the participant had others present, and observations during the process of the consent (e.g. discussion by the participant with an attendant or family member)

If women are unconscious or in a mental state where they are unable to consent for themselves, an attendant or guardian will be approached for consent. As women in this condition are at high risk for morbidity and/or mortality inclusion in this study is key to achieve the objectives of reducing this risk. Additionally, women in this condition are the most likely to gain direct benefit from vital sign monitoring. As such if an attendant is not available the woman will be enrolled without consent to enable monitoring to begin immediately. Consent will be sought as soon as possible after the woman regains capacity to consent or an attendant becomes available. If the woman and/or her attendant declines to participate at that time all study procedures will be discontinued.

Study Procedures

1. A group meeting detailing the study background, procedures, risks and benefits will be held for all clinical providers in the department prior to study initiation.
2. We will obtain informed consent for clinicians and peripartum women admitted for delivery as described above.
3. A 2-hour training session on the use of the wireless monitoring system, nature of alerts and emergency mobile phone will be held for enrolled clinicians at a time convenient to them.
4. Alternative two-week blocks will be assigned to “intervention” vs “control”. During an “intervention block” all women delivering by emergency cesarean and consenting to participate will be monitored using the wireless device for the first 24 hours after delivery. During a “control

block" standard of care for monitoring will be used and women delivering via emergency cesarean will have record review only.

5. Maternity ward coverage schedules for enrolled specialist and midwives will be obtained. This will be used to determine the clinicians on call during each intervention block.
6. During the intervention block, midwives present in the theatre will be asked to perform the following tasks for any emergency cesarean deliveries s/he is present for:
 - a. Placement of the biosensor on any enrolled women s/he delivers by emergency cesarean delivery immediately after completion of the surgery.

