On average approximately 8-10 emergency cesarean deliveries are performed at MRRH daily. Thus, in a two week block we estimate ~ 112 emergency cesareans performed. We plan to capture all women delivered by emergency cesarean during an intervention block thus minimizing the risk of selection bias based on the severity level. Assuming 85% of women consent to participation (conservative estimate based on >90% recruitment in prior studies)^{5,74,75}, this yields an estimated 95 women per block. Over 12 months of enrollment, we will therefore have 13 intervention blocks and 13 control blocks. This yields an estimated 1,235 women in the intervention group and 1,235 in the control group. Assuming an intraclass correlation coefficient of 0.01, the effective sample size after taking account of clustering is 633 per group. This will allow us to detect a difference of 5.7% in the SMO rate between the two study arms, with a two-sided significance level of 0.05, and 80% power, assuming a baseline rate of SMO of 13% ^{71,73}

Risk/Discomforts and protections

Clinicians:

- Risk of false alerts, alert fatigue: Clinicians will be asked to hold a mobile phone and respond to alerts. It is possible that alerts of physiologic sign abnormalities may not correspond to a developing or established clinical abnormality and in responding to the alert clinicians may become fatigued from alerts. Study investigators will monitor for this occurrence and the impact on clinician performance and duties and adjust study protocols as necessary
- Risk of diversion and interruptions to work on other patients: Alerts sent to clinicians may also prompt them to perform additional exams or clinical procedures that may or may not be beneficial to the patients from which alerts were received. This may divert attention or human resource away from other clinical needs. We will monitor for any diversions resulting in substandard clinical care. If these occur we will consider protocol modifications. Any safety concerns or adverse events arising because of false alerts or diversions will be communicated to the IRB within 10 days.

Peripartum women:

- Theoretical risk of exposure to radio emissions from Wi-Fi from the biosensor: There is a theoretical risk of exposure to Wi-Fi signals from the biosensor worn by women participating in

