#### Protocol Deviations

Protocol deviations will be summarized in frequency tables

**Aim 1: To estimate the clinical effectiveness of wireless physiologic monitoring of women in the first 24 hours after cesarean delivery**

**Exposure** Intervention arm

**Primary outcome** Severe Maternal Outcome

**Endpoint** Discharge from hospital

**Descriptive statistics:** Proportion of women with one or more SMO, overall and by arm.

**Inferential statistics:** SMO will be statistically compared by arm using a Poisson model.

An intention to treat approach will be used to assess effectiveness. Thus, all women eligible for monitoring during an intervention arm including those who 1) declined consent 2) were missed from screening 3) were screened and not enrolled 4) enrolled but did not receive the intervention will be included in the intervention. The event rate for the primary and secondary outcomes will be calculated during the intervention and control time periods on all eligible women during those time periods. While intervention allocation was at the level of the two-week time period, the analysis will be at the individual patient level adjusting for clustering of observations within time periods. Using a logistic regression mixed effects model, with random effects to account for time block, we will compare the rate primary outcome between the intervention and control time periods.

Exploratory analyses will be used to determine if the intervention has a more significant effect in certain sub- groups of women (e.g. women <35, or women with more education). The interaction between study arm and comorbidities (i.e., HIV, hypertension, pulmonary, cardiac or kidney disease, malaria) will also be tested in logistic regression models. Subgroup effects will be reported if there is strong evidence of heterogeneity of intervention effect.

**Commented [BAA3]:** Intervention time periods will include women who  
-Declined consent  
-Were missed from screening  
-Were screened and unable to enroll  
-Enrolled but did not get the “full intervention”  
-Screened and enrolled – deceased before monitoring  
-Women ineligible due to language but those women will not be known in the control group.

**Commented [BAA4]:** Random effects for week using a mixed effects model  
Vs GEE where you put in clustering or correlation

**Commented [BAA5]:** Account for missing data in control period  
- impute for variables that are available and are independent for the intervention  

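### The SAP calls the design an interrupted time series, but no stated primary model includes calendar time, so any drift over the year would widen the confidence interval

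*SAP*

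**What the plan says.** The SAP (Study Objectives and Summary) labels the design a "quasi-experimental, interrupted time series with repeated on/off periods" and gives the arms as "Repeated on/off intervention-control periods in 2-week blocks". Protocol, Study Procedures, item 4 says: "Alternative two-week blocks will be assigned to" intervention or control. Neither document mentions a random order of blocks or says which arm starts.

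Protocol, Sample Size plans 12 months of enrolment: "we will therefore have 13 intervention blocks and 13 control blocks", and "this yields an estimated 95 women per block".

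Three models are named for the primary outcome:

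- SAP, Aim 1 inferential statistics, first statement: a Poisson model by arm.
- The same section, second statement: a logistic mixed model "with random effects to account for time block".
- Protocol, Biostatistical Analysis, Aim 1: logistic regression by GEE, with time blocks as clusters.

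None has a fixed term for trend or season. A SAP margin comment weighs random effects against GEE but does not raise calendar time. Change over time is examined only under the Aim 2 Maintenance metric.

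**The concern.** An interrupted time series normally uses the order of its periods. A random block effect, or GEE clustering on block, treats the 26 blocks as exchangeable, so the fact that block 1 came a year before block 26 plays no part. If the rate of severe maternal outcome (SMO) moves over the year, whether through season, staffing or referral pattern, that movement is counted as unexplained block-to-block variation. The plan already accepts a design effect near 2 for that variation, and a time term could recover part of it.

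A second question comes from the fixed order. Two weeks on and two weeks off repeats every 28 days, so a ward cycle of exactly that length would line up with arm.

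**Working it through.** **Inputs.** From Protocol, Sample Size: 26 blocks, 95 women per block, 13% SMO, and "Assuming an intraclass correlation coefficient of 0.01". Assumed: linear drift of 6 or 10 points between the first and last block.

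**The plan's own figure.** The design effect is 1 + 94 × 0.01 = 1.94, and 1,235 / 1.94 = 637 per arm. Using 1 + 95 × 0.01 = 1.95 gives 633, the stated value. The plan's clustering arithmetic is reproduced.

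**Bias from drift.** With strict alternation the arms are on average one block apart in time. Drift of D over the 25 steps gives a bias of D/25: 0.24 points for D = 6 and 0.40 for D = 10. If D is counted over the full 52 weeks, this is D/26.

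**Variance of a block's observed rate, in squared percentage points.**

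- Between blocks: 0.01 × 0.13 × 0.87 × 10,000 = 11.3 (SD 3.4 points).
- Binomial: 0.13 × 0.87 × 10,000 / 95 = 11.9.
- Sum: 23.2.
- Drift left in the error: (D/25)² × 58.5, where 58.5 = 26 × 27 / 12 is the variance of block number. This is 3.37 at D = 6 and 9.36 at D = 10.
- Implied ICC including drift: (11.31 + 3.37) / 1,131 = 0.0130 and (11.31 + 9.36) / 1,131 = 0.0183, where 1,131 = 0.13 × 0.87 × 10,000.

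**Cost of linear and quadratic time.** The t quantile rises from 2.064 (24 df) to 2.074 (22 df), a factor of 1.005. The arm–time correlation is −0.067, giving a factor of 1/√(1 − 0.0044) = 1.002. The quadratic term is symmetric about mid-year and adds nothing further. The product is 1.007, so the cost is under 1%.

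**95% half-width of the arm difference**, t × √(variance × 2/13):

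| Drift over the year | Without time | With time | Change |
|---|---|---|---|
| none | 3.90 | 3.93 | 0.7% wider |
| 6 points | 4.17 | 3.93 | 6% narrower |
| 10 points | 4.62 | 3.93 | 15% narrower |

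A block-level simulation agrees: under 1% wider, then about 6% and 16% narrower.

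**False positives with no true effect.** In simulation, the logistic random-block model without a time term rejects 6.8% of the time with no drift, 4.1% at 6 points and 3.0% at 10 points. The block-level analysis gives 3.5% and 2.2% at 6 and 10 points. Drift makes the test conservative.

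**Simulated power**, logistic random-block model, downward drift, linear term only (Monte Carlo SE up to about 2 points):

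| True difference | Drift | Without | With |
|---|---|---|---|
| 5.7-point reduction | none | 87.6% | 88.8% |
| | 6 points | 84.4% | 91.4% |
| | 10 points | 71.8% | 90.8% |
| 5.7-point increase | none | 82.0% | 82.8% |
| | 6 points | 80.2% | 79.8% |
| | 10 points | 75.0% | 80.2% |

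Two cautions apply. With the linear term, the likelihood-ratio test rejects 6.1% to 7.4% under the null, so part of the gain is the loss of conservatism. A reduction combined with a large downward drift brings rates near 2%, so those figures are approximate. The interval widths are the cleaner measure.

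**Sensitivity to block size.** The SAP gives 1,266 women in total. If these are enrolled women, blocks hold 633 / 13 = 48.7. The binomial part becomes 1,131 / 48.7 = 23.2 and the sum 34.5. The ratios are √(34.5/37.9) × 1.007 = 0.96 and √(34.5/43.9) × 1.007 = 0.89, so the gain falls to about 4% and 11%.

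**Cycles.** Over 26 alternating blocks, a sinusoid of amplitude A and period 28 days produces a false arm difference of up to 1.28A, depending on phase. A calendar-month cycle gives at most 0.04A and an 8-week cycle 0.10A. Cycles of 13 weeks, half a year and a year give about zero. In simulation with no true effect, a 2-point difference between alternate blocks gives 21.7% false positives without a linear time term and 22.6% with it. A 3.8-point difference gives 54.2% and 54.6%.

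**The case against.** The case for leaving the plan alone is substantial. The design is openly quasi-experimental, and alternation with clustering on block is coherent: it already protects the estimate from smooth drift, and the test stays valid. The documents give no drift size. With no drift the power differences are within simulation error, and with a 5.7-point increase and 6 points of drift there is no gain. A quadratic would not follow a sudden staffing change or a full seasonal cycle. All of this stands. It limits the point to precision but does not remove it, because the cost of the terms is under 1% of interval width.

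A reader might infer more in three ways:

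- **That drift biases the result or raises type I error.** The calculations show negligible bias and fewer rejections. This holds for analyses that account for block; the SAP's Poisson sentence alone names no clustering, but the text after it requires that adjustment.
- **That the detectable reduction would fall from 4.8 points to between 4.5 and 4.2.** This takes smooth calendar variation to be a quarter to a half of the block variance. Setting D²/12 equal to a quarter or a half of 0.00113 requires D of about 5.8 to 8.2 points in one year on a 13% baseline. Nothing in the documents supports that.
- **That arm is confounded with a staff rota.** No 28-day rota or other four-week cycle is described. The protocol collects coverage and call schedules (Study Procedures, items 5 and 9) and plans an exploratory comparison of providers. These could not undo exact alignment, but they allow it to be looked for.

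Randomising the block order may also no longer be possible. The SAP, dated September 2021, describes allocation by two-week period in the past tense, so blocks may already have run.

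**Conclusion.** The gap is real and is one of efficiency. No stated primary model uses calendar time, so any drift over the 12 months enters the between-block error, widens the interval and makes the test conservative. Prespecified linear and quadratic time would cost under 1% of interval width if there is no drift. It would save roughly 6% at 6 points and 16% at 10 points of linear drift, or about 4% and 11% if blocks hold 49 women. These sizes rest on the protocol's ICC and baseline rate and on assumed drift.

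The 28-day alignment is a property of strict alternation, but with no such cycle reported it is a vulnerability to check, not a demonstrated bias.

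**What to change.** 1. In SAP, Aim 1 inferential statistics, prespecify block start date, linear and quadratic, as fixed effects in the primary model. Keep the block random effect, or GEE clustering if that is the model chosen. The cost is one sentence and 2 degrees of freedom out of 26 blocks. It should be settled before outcomes are compared by arm, since adding time afterwards would look data-driven.
2. Check the coverage and call schedules for a cycle of exactly 28 days. Report what is found, and state as a limitation that alternation could not separate such a cycle from arm. This uses schedules that the protocol already has the study obtain.
3. Only if blocks remain to be run, draw at random which block of each consecutive pair is the intervention block. The cost is a short allocation list and the occasional adjacent pair of same-arm blocks. It would not give randomisation-based inference for blocks already alternated.

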## General Analytic Considerations

### Data sources

Data are to be derived from the following:

1. Electronic data entry of questionnaire into REDCap
2. Electronic data entry of chart review into REDCap
3. Survey data from Midwives into Redcap
4. Vital sign data from Current Health devices
5. Alarm data from Current Health devices.

NCT ID: 2019P000885

Document Date: September 26th 2021

#### Test size and confidence levels

Analyses, including the primary analysis, will be based on two-sided  $\alpha=0.05$  level tests and 95% confidence intervals (CIs). No adjustment will be made for multiple comparisons.

#### Study size and Power

With 1266 enrolled participants, assuming an expected severe maternal outcome (SMO) rate of 13% in the control arm and intraclass correlation co-efficient of 0.01, will provide 80% power using a 2-sided  $\alpha=0.05$  to detect a difference of 5.7% in rate of SMO between the two groups.

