The wireless monitor to be used is a wearable wireless vital sign monitor called Current™. The device provides continuous real-time transmission of oxygen saturation, respiration rate, pulse rate, temperature, motion and activity, and posture captured every 2 seconds. It is integrated with the Omron Evolv blood™ pressure cuff to allow automated capture of blood pressure. Physiologic data from the sensor is transmitted via WiFi to a secure cloud storage (hosted by Amazon Web Services). Current™ is fully HIPAA¹ compliant and HITRUST² certified and has received US FDA approval. Physiologic data can then be accessed via a secure password protected mobile phone app or displayed on a monitor for real-time viewing. Pre-defined criteria can be used to program alerts or notifications should vital signs fall outside of the range. These notifications can be received via SMS or a mobile app notification. Notifications can be sent to multiple providers at a time. Providers can also log on or off from the device corresponding to their duty shifts.

To complete Aim 1, we will enroll all willing attending doctors and staff midwives with clinical duties covering the maternity ward, emergency cesarean delivery and postoperative care during the study period to use the wireless physiologic system and receive message alerts. Due to staffing the numbers of clinicians may fluctuate during the enrollment period. We will also enroll 1235 women undergoing emergency cesarean delivery during the study period during intervention blocks to wear a wireless physiologic monitor for 24 hours after birth. An additional 1235 women, also undergoing emergency cesarean during the study period during non-intervention blocks, will form a control group and have medical record review only. *We request to waive consent for this record review only.* Clinicians and peripartum women participating in wireless physiologic monitoring will form the same participants for Aim 2, which will involve participant observation, record review, and retrieval of data from the wireless monitoring system and clinician responder phones. To complete Aim 3, We will perform semi-structured interviews on 30 clinicians and 30 postpartum women drawn from

¹ HIPAA: Health Insurance Portability and Accountability Act of 1996) is United States legislation that provides data privacy and security provisions for safeguarding medical information

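### The SAP reports the protocol's effective sample size (633 per arm) as women enrolled, and neither power statement says whether the 5.7-point difference is a fall or a rise

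*SAP*

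**What the plan says.** **Protocol, Sample Size.** Two-week blocks of about 95 consenting women are planned: "Over 12 months of enrollment, we will therefore have 13 intervention blocks and 13 control blocks". From this, "This yields an estimated 1,235 women in the intervention group and 1,235 in the control group". With an intraclass correlation of 0.01, "the effective sample size after taking account of clustering is 633 per group. This will allow us to detect a difference of 5.7" percentage points, at two-sided 0.05, 80% power and a baseline severe maternal outcome (SMO) rate of 13%.

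**Protocol, Study Intervention and Study Population Overview.** The 1,235 is used as a count of women: "An additional 1235 women, also undergoing emergency cesarean during the study period during non-intervention blocks, will form a control group". The overview table totals 2,522 people.

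**SAP, Study Objectives and Summary.** The sample size is "Approximately 1266 women (633 per arm); dependent on clinical volume during blocks", under a design described as "Repeated on/off intervention-control periods in 2-week blocks".

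**SAP, Study size and Power.** The section opens by calling the same total an enrolled count: "With 1266 enrolled participants, assuming an expected severe maternal outcome (SMO) rate of 13% in the control arm and intraclass correlation co-efficient of 0.01". It then claims 80% power at two-sided 0.05 for a difference of 5.7 points.

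Neither power statement gives an intervention-arm rate or a direction. The intended direction appears elsewhere in the protocol: Specific Aim 5 counts outcomes averted, and the analysis of Aims 4 and 5 refers to reducing SMO.

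**The concern.** An effective sample size is what remains after the head count has been divided by the design effect. The SAP takes the figure that the protocol had already discounted, calls it enrolled women, and quotes the same intraclass correlation beside it. The two documents therefore attach one power claim to two enrolment targets.

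This matters for reporting. The SAP plans a disposition flow diagram, and the data and safety monitoring board is asked to follow study progress. Against the SAP, 1,266 women would be full recruitment; against the protocol, about half.

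The missing direction is a separate point. With a control rate of 13%, a fall and a rise of equal size have different variances, so 5.7 points has different power each way. A null result would be read against a detectable effect that is not the smallest reduction the planned design can detect.

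**Working it through.** **Inputs.** From the protocol's Sample Size section: 95 women per block, 13 blocks per arm, ICC 0.01, control rate 13%, two-sided 0.05, 80% power, 5.7 points. From the SAP: 633 per arm, 1,266 in total, all else the same.

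**1. Is 1,235 a head count?** 13 × 95 = 1,235. In the overview table, 52 clinicians + 1,235 + 1,235 = 2,522, which is the stated total. Yes.

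**2. Where does 633 come from?**
- Usual design effect: 1 + (95 − 1) × 0.01 = 1.94, and 1,235/1.94 = 636.6.
- With 1 + 95 × 0.01 = 1.95: 1,235/1.95 = 633.3.

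The protocol's 633 reproduces with 1.95; the difference from 637 is immaterial. Then 2 × 633 = 1,266, the SAP's enrolled total.

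**3. Which direction gives 5.7 points at 80% power?** Pooled two-proportion formula with n = 633 effective per arm:

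power = Φ{ [d − 1.96·√(2p̄(1−p̄)/n)] / √([p₁(1−p₁)+p₂(1−p₂)]/n) }

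- Rise, 13% to 18.7%: p̄ = 0.1585; (0.057 − 1.96 × 0.02053)/0.02047 = 0.819; power 79.4%.
- Fall, 13% to 7.3%: p̄ = 0.1015; (0.057 − 1.96 × 0.01697)/0.01690 = 1.404; power 92.0%.

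Solving for 80% power gives a detectable rise of 5.75 points and a detectable fall of 4.84 points (13.0% to 8.2%). Unpooled and arcsine versions give 79.5% to 79.6% for the rise, so the choice of formula does not change the answer: the protocol's figure corresponds to an increase in SMO.

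**4. What if the SAP's 633 per arm really is enrolment?** It must then be discounted for clustering.

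| Reading | Women per block | Design effect | Effective n per arm | Power, 5.7-point fall | Power, 5.7-point rise | Detectable fall |
|---|---|---|---|---|---|---|
| Protocol: 1,235 per arm, 13 blocks | 95 | 1.95 | 633 | 92.0% | 79.4% | 4.84 |
| SAP: 633 per arm, 13 blocks | 48.7 | 1.48 | 429 | 79.0% | 62.8% | 5.76 |
| SAP: 633 per arm, blocks of 95 | 95 | 1.94 | 326 | 67.5% | 51.3% | 6.50 |

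The second row assumes that all 26 blocks are run at about half the protocol's volume. The third assumes that accrual stops after about 13.3 blocks (1,266/95), which neither document says.

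**5. Side by side.** The evidence for a mislabel is that the same 633 recurs with identical ICC, control rate, power and difference, with no new block count, cluster size or derivation in the SAP. It is not that the SAP's sentence fails arithmetically: the second row comes within a point of 80% for a fall.

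**The case against.** The strongest reply is that the SAP's sentence nearly works as written. With 633 enrolled per arm over 13 blocks, power for a 5.7-point fall is 79.0%. The SAP also calls its total approximate and dependent on volume, and about 49 women per block would fill 12 months. That 633 was copied is therefore an inference. This stands, and for the same reason the SAP's 12-month period does not separate the two readings. But a near-match in one unstated direction does not reconcile 2,470 with 1,266, and volume-dependence does not explain a total that is exactly twice the protocol's effective size.

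Second, the consequence is small. Accrual is by calendar block, the SAP analyses all eligible women in each period, and neither total enters a test, an estimate or a stopping decision. That stands too, and it limits the weight of the point.

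Third, the direction can be inferred from the aims, the test is two-sided, and 5.7 points is conservative for a reduction. That is true at the protocol's size. The stated figure is still not the design's detectable reduction.

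Fourth, 4.8 points comes from a large-sample formula although only 26 blocks are allocated. With a t reference on 24 degrees of freedom (an assumption, with unpooled variance), the detectable fall is about 5.0 points and power for a 5.7-point fall about 90%. This deserves a note beside the figure; it does not bring 5.7 back as the detectable reduction.

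**Conclusion.** The concern holds and should be fixed. The SAP's stated enrolment is about half the protocol's (1,266 against 2,470) under one power statement, and the SAP's figure equals twice the protocol's effective size per arm. At that effective size the 5.7-point difference matches a rise in SMO. For the intended fall, the detectable difference is about 4.8 points and power for 5.7 points is 92.0%.

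These figures rest on the protocol's own inputs (ICC 0.01, 95 per block, 13% control rate) and a large-sample two-proportion test on effective size. The documents give no range for the ICC, so none is applied here.

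This corrects the stated design; it does not show an underpowered trial. Power would fall to 67.5% for a 5.7-point reduction only if accrual stopped at 1,266 in blocks of 95, and neither document plans that.

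**What to change.** 1. In the SAP (Study Objectives and Summary; Study size and Power), give planned enrolment as about 2,470 women (1,235 per arm, 13 two-week blocks per arm of about 95) and label 633 per arm as the effective size. State the design effect used: 1.95 gives 633, 1.94 gives 637.
2. If 1,266 is the real target, say so, with its block count and its detectable reduction (about 5.8 points over 26 blocks), and reconcile the protocol.
3. In both documents, state that the difference is a reduction and give the detectable reduction as about 4.8 points (13.0% to 8.2%). Name the formula and note that a t reference on 24 degrees of freedom gives about 5.0.
4. Optionally, note that the all-eligible set in the SAP's Aim 1 analysis is larger than the consenting 1,235. Its size is an assumption. The protocol says "On average approximately 8-10 emergency cesarean deliveries are performed at MRRH daily", which is 112 to 140 per block, or 1,456 to 1,820 per arm over 13 blocks before eligibility criteria. With design effects of 2.11 and 2.39, the effective sizes are about 690 and 762 and the detectable falls about 4.65 and 4.45 points.

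Items 1, 3 and 4 are wording only: no extra women and no change to accrual, outcome or model. Item 2 would be a real change to planned enrolment and should be recorded as one.
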